Targeting Self-regulatory Deficits Through Cognitive Remediation Intervention

NCT03373240

March 22, 2019

HRP-503B – BIOMEDICAL RESEARCH PROTOCOL
(2016-1)

Protocol Title: Targeting self-regulatory deficits through cognitive remediation intervention

Principal Investigator: [name]

Version Date: 03022019

(If applicable) Clinicaltrials.gov Registration #: Click or tap here to enter text.

INSTRUCTIONS

This template is intended to help investigators prepare a protocol that includes all of the necessary information needed by the IRB to determine whether a study meets approval criteria. **Read the following instructions before proceeding:**

1. Use this protocol template for a PI initiated study that includes direct interactions with research subjects. Additional templates for other types of research protocols are available in the system Library.
2. If a section or question does not apply to your research study, type “Not Applicable” underneath.
3. Once completed, upload your protocol in the “Basic Information” screen in IRES IRB system.

SECTION I: RESEARCH PLAN

1. **Statement of Purpose:** State the scientific aim(s) of the study, or the hypotheses to be tested.

Version Date: 03022019

Version 3

The overarching objective of this supplement application is to apply a behavioral medicine approach to validate a novel set of interventions that may be used to both study and treat cognitive-affective dysfunctions implicated in self-regulation. By systematically characterizing and addressing cognitive-affective processes, we aim to accelerate assessment and treatment efforts in disorders characterized by dysfunction in self-regulation, including substance use disorders (SUDs). The proposed research will evaluate the possibility of modifying cognitive-affective deficits that hinder self-regulation using a focused skill-building approach targeting three domains demonstrated to be disrupted in SUDs: executive function, negative emotionality, and incentive salience.

We are proposing a small randomized clinical trial in which 100 substance users will complete the existing Psychotherapy Development Center (PDC) pretreatment assessment battery as well as a novel battery of assays to evaluate cognitive-affective functioning. These batteries will be administered before and after the intervention (cognitive training tasks) to help examine the generalizability of any training effects to related cognitive training tasks (tasks that the participant was not specifically trained on). These related tasks will also help quantify participants' potential responsiveness to treatment and, as such, may help bridge the gap between behavior, mechanism, and treatment.

After completing pretreatment assessments, participants will be randomized to either a (1) cognitive remediation program (training tasks) specifically designed to address cognitive-affective dysregulation or (2) control tasks (verbal fluency tasks). Tasks will be completed twice per week for 4 weeks, after which assessment batteries will be repeated. Finally, we will evaluate real-world behavior and the durability of the training via a one-month follow-up, which will include assessment of substance use as well as the cognitive-affective battery. Our primary Specific Aim will be to evaluate the efficacy of the cognitive-remediation program relative to the control condition control on the indicators of cognitive-affective functioning and substance use, testing the hypothesis that individuals randomized to the cognitive remediation program will demonstrate improved functioning on the cognitive-affective battery as well as reduced substance abuse. We will also explore potential moderators of response to the training, including baseline measures of cognitive-affective function.

Our long term goal is to enhance outcomes of effective 'top down' treatments like cognitive behavior therapy (CBT) and contingency management by combining them with brief 'bottom up' interventions that address, more directly, underlying mechanistic deficits that impact self-regulation and ultimately the maintenance of SUDs. The proposed research will lay the foundation for a more thorough evaluation of 'mechanism matched cognitive remediation' (1). Translation of these findings is expected to eventually allow clinician to match cognitive remediation interventions to the respective core deficits of their patients. Targeted intervention strategies such as these are likely to improve outcomes for multiple externalizing disorders, including SUDs. Moreover, as they are brief and administered via computer, the potential dissemination of these treatments could be more efficient, cost-effective, and implemented in a wider variety of settings (e.g., primary care, rural areas) than traditional behavior change interventions.

2. **Probable Duration of Project:** State the expected duration of the project, including all follow-up and data analysis activities.

Two years

3. **Background:** Describe the background information that led to the plan for this project. Provide references to support the expectation of obtaining useful scientific data.

Cognitive-Affective factors and substance use disorders (SUDs):

SUDs rank among the most widespread and costly illnesses in the US (17, 18). Although multiple factors contribute to the development and maintenance of SUDs, core neurobiological and psychological processes are commonly implicated in the development and maintenance of SUDs and other externalizing disorders (e.g., antisocial personality, attention deficit-hyperactivity, conduct). In particular, these disorders are characterized by marked dysfunction in self-regulation, suberved by impairments in executive function and hyper-reactivity of negative emotionality and incentive salience (19, 20). Dysfunctions in these domains are mirrored in the tendency for individuals with SUDs to demonstrate strong attentional orienting to motivationally salient cues (21), failure to inhibit reward seeking responses (22), difficulty classifying rare or unexpected stimuli in the oddball task (23), deficits in distress tolerance (24), and poor delay discounting during gambling tasks (25). In these instances, individuals with SUDs react strongly to motivationally salient information (e.g., unexpected information, goal-relevant reward, punishment, threat), particularly when they are prepared to make a practiced, dominant response. Accordingly, reactivity to affective information (incentive or negative emotion) and deficiencies in executive function may disinhibit individuals with SUDs to engage in pleasure-seeking (e.g., substance use), display extraverted interpersonal tendencies, and to act in an impulsive manner, particularly when in an affectively charged situation. Thus, interventions that directly target these underlying cognitive-affective deficits are a novel and promising strategy to enhance intervention effectiveness.

Translating mechanism into intervention:

Cognitive-affective impairments are a persistent and functionally relevant feature of multiple disorders, including SUDs (26-30). Such impairments span multiple domains and are more closely linked to functional outcomes than severity of clinical symptomatology, making them a priority for treatment development (27, 28, 31, 32). Increasingly, there is strong interest in understanding the mechanisms of behavior change and developing effective interventions that capitalize on this understanding (3). One promising and innovative intervention strategy is cognitive remediation. Cognitive remediation encompasses a diverse array of “interventions that aim to improve (neuro)cognitive functions (attention, memory, executive function, social cognition, or metacognition) with the goal of durability and generalization” (33). Some evidence suggests the promise of this approach for SUDs (34, 35), although early efforts to use this treatment approach for SUDs has failed to assess the translation of specific skills to generalizable skills. Additionally, most of this early work has either provided non-specific training (e.g., general executive functioning or attention bias modification) or training on a single dysfunction (e.g., distress tolerance) that did not necessarily capitalize on our understanding of the multifaceted cognitive-affective deficits affecting individuals with SUDs. Recent research suggests it is possible to identify cognitive-affective processes that are dysfunctional in SUDs and related disorders, target those cognitive-affective processes, and bring about change in those processes using a systematic approach to cognitive remediation tailored to specific self-regulatory deficits: Co-investigator [name] (1) designed a cognitive remediation program for incarcerated individuals with SUDs (see Preliminary Studies). This program was developed to target specific cognitive-affective deficits in two antisocial

subtypes (psychopathic and externalizing) with co-morbid SUDs. There is a large body of evidence suggesting that individuals with psychopathy + SUDs are characterized by impairments in modulating attention to accommodate multiple streams of information, whereas individuals with externalizing/antisocial personality disorder + SUDs demonstrate exaggerated responses to affective information and various kinds of motivational cues, in combination with reduced regulatory capacity (36). Training that used a multi-task package designed to target the specific cognitive-affective deficits associated with either subtype (psychopathic versus externalizing) led to improvement on both trained and non-trained tasks, with improved outcomes for individuals who received the type of training tailored to the deficits associated with their subtype. This SOBC supplement would extend this work by testing the cognitive remediation strategy used for the externalizing subtype in a heterogeneous sample of individuals with substance use disorders.

[name] recently published cognitive remediation study in offenders (1) represents a proof of concept study for the proposed SOBC supplement (see Figure 1). Training designed to target affective self-regulation and remedy the distinct deficits associated with SUD-offender subtypes resulted in specific and differential improvement on trained and non-trained tasks. Moreover, analyses demonstrated that using three tasks to tap cognitive-affective dysfunction from multiple angles was a stronger predictor of change than any single task. Finally, unpublished analysis showed that individuals who received training that matched their cognitive-affective deficits had fewer disciplinary reports in prison two months following the training. Together, these tasks highlight the utility of targeting cognitive-affective functions through targeted computerized tasks and the generalizability of change to other tasks and to real-world behavior.

[figure not shown]

Figure 1. Overview of study design, Baskin-Sommers et al (2105). Proposed SOBC project uses cognitive remediation tasks targeted for improved affective-cognitive control (boxed area)

4. **Research Plan:** Summarize the study design and research procedures using non-technical language that can be readily understood by someone outside the discipline. **Be sure to distinguish between standard of care vs. research procedures when applicable, and include any flowcharts of visits specifying their individual times and lengths.** Describe the setting in which the research will take place.

Overview:

The proposed SOBC supplement project will be conducted at the Substance Abuse Treatment Unit (SATU) and Adult Outpatient Psychiatric Services (IOP) in New Haven. One hundred substance

Version Date: 03022019

Version 3

users will be randomized, via a computerized urn randomization program (55) we have used in multiple previous trials (9, 10, 37, 56, 57) to either the cognitive remediation package or a control condition (computerized verbal fluency tasks), with trainings conducted twice per week for 4 weeks. Training will be conducted as an add-on to the participants' ongoing standard treatment at the clinic.

Several variables will be assessed. Demographic variables will include gender, race, and level of education. Person-specific variables will include type and severity of substance use disorder, personality characteristics, and treatment readiness. Pre- and post-training testing will evaluate change in cognitive-affective targets, with a one-month follow-up period to evaluate both the durability of training effects as well as impact on real-world behaviors (substance use).

This project will benefit the Parent award (P50 DA 0009241) by enabling us to evaluate how individuals with varying levels of these cognitive-affective deficits respond to study interventions and hence inform future projects which could address whether addressing these deficits via cognitive remediation improves response to empirically validated therapies via 'mechanism-matched' cognitive remediation.

Diagnostic and Baseline Assessments:

After providing written informed consent (see Human Subjects), participants will complete the following components of the Parent award (Psychotherapy Development Center, PDC) Core assessment battery to facilitate comparison with ongoing/previous Center studies:

- *Structured Clinical Interview for DSM-5 (SCID)* (58) (59), including antisocial personality disorder.
- The *Brief Symptom Index (BSI)* (60) is a widely used 53-item inventory of psychiatric symptoms.
- *Substance Use Calendar*. Self-reports of substance use (cocaine, alcohol, opioids, marijuana, other illicit drugs, and nicotine) are documented at each contact via the Substance Use Calendar. Similar to the Time Line Follow-Back (61), the Substance Use Calendar assesses substance use on a daily basis.
- *State-Trait Anxiety Inventory (STAI)* is a widely-used measure of consistent and transient stress and anxiety (62).
- *Distress Tolerance*. (24, 63, 64) is commonly measured using the Mirror Tracing Persistence Task (65).
- *Shipley Institute of Living Scale* (66) is included as a widely used measure of general intelligence.
- *Balloon Analog Risk Task (BART)* is a computerized measure of risk-taking (67).
- *Five-trial adjusting delay discounting task* is a brief computerized measure of delay discounting (Koffarnus & Bickel, 2014).

Baseline Cognitive-Affective Assessments:

This battery includes three tasks that have been previously used to tap the cognitive-affective processes associated with SUDs and other externalizing disorders.

- *Incentivized n-Back task* includes manipulations of working memory load, response prepotency, and incentivized performance (trial-by-trial feedback using monetary reward and punishment) to examine the integrity of cognitive control functions necessary for successful regulation of behavior. In this task, participants view a series of letters. Participants are instructed to monitor the letters and

Version Date: 03022019

Version 3

respond with a button press if the preceding letter in the *n*-back position is different from the current letter (e.g., a mismatch trial). Participants are instructed to withhold their response when the preceding letter matched the current stimulus (e.g., a match trial). The majority of trials are mismatch trials (80%), whereas match trials are infrequent (20%). The task also includes a manipulation of working memory load. In the low load (1-back) condition, participants are instructed to determine whether the currently presented letter matched the immediately preceding letter in the sequence. In the high load (2-back) condition, participants are required to monitor and maintain the stimulus information in working memory in order to determine whether the letter stimulus 2 positions earlier matched the current letter. Finally, the task manipulates incentives on a subset of trials; in separate blocks participants received reward (sound of a coin drop and the addition of 5 cents) following a correct response or punishment following an incorrect response (aversive .5s 100dB noise blast and the loss of 5 cents). The primary dependent variable will be task performance. The Incentivized *n*-Back task is thus used to assess relevant processes because deficits because it evaluates a person's tendency to over-allocate attention to motivationally-salient information (22, 74).

Post-Treatment Follow- Assessments:

At the end of the 4 weeks, the participant will be asked to fill out more questionnaires (see table below), provide a urine and breath specimen for drug and alcohol testing, and be interviewed again. This assessment session will take about 1 hour.

Study assessments schedule:

Instrument/task	Rater	Screen	Week 0	Training	Week 4	Follow-up
Informed consent quiz	P	x				
Demographics and medical history	P	x				
Locator form	RA					
SCID for DSM-5	RA	x				
Shipley	P	x				
Inclusion/exclusion	RA	x				
Urn randomization	RA	x				
Utox and BAC	RA	x	x	x	x	x
BSI	P		x		x	x
Substance Use Calendar	RA		x	x	x	x
State-Trait Anxiety	P		x		X	x
Distress Tolerance	RA		X		X	x
BART	RA		X		X	x
5-Item Delay Discounting	RA		X		X	X
Incentivized n-back	RA		X		X	X
Externalizing Spectrum Inventory	P		x			
Perceived Stress Scale	P		x			x
Circumstance, Motivation, Readiness Scale for Treatment	P		x			x

Interventions:

Version Date: 03022019

Version 3

Participants will be randomized to one of 2 training conditions, to be completed twice per week over 4 weeks, *in addition* to standard treatment at SATU/IOP, which typically consists of weekly group meetings, case management and random urine toxicology screening. Each training session will be 30-45 minutes (time variability depends on speed of reading instructions and choices made in the tasks). Across all weeks the participant will complete approximately six hours of training.

Control condition. Participants randomized to this condition will complete a computerized verbal flexibility task (Text Twist). An active computer-based control was selected as it provides a rigorous comparison to intervention and will help address concerns that any game-style activities will produce improvements by controlling for computer time and game experiences, as well as non-specific elements such as support, attention, study contact, activation, and motivation. It is possible an active and engaging control condition may produce modest neurocognitive change in some domains, but available data indicate the control condition is not likely to influence the target-specific processes associated with self-regulation (75).

Cognitive Remediation tasks: The target training focuses on providing individuals with practice inhibiting, learning, and making decisions *within affective contexts*. Well-validated tasks that have been reliably shown to tap these processes, and are amenable to repeated administration, were selected. Each of these tasks taps the underlying domains of self-regulatory dysfunction (executive function, negative emotionality, incentive salience). Thus, this training package more directly builds on previous work that establishes the importance of *dual demands on cognitive and affective processes associated with regulation of behavior*. Moreover, it addresses the complex cognitive-affective dysfunctions in self-regulation from multiple angles rather than targeting or tapping a single process that is likely entrapped within a more multi-faceted dysfunction. The basic structure of this training has been successfully implemented in [name] previous work (1). The three tasks will address inhibition in the face of reward, cost-benefit decision-making in the face of uncertainty, and working memory in the face of distress. These three tasks provide measures of the target processes of interest, but are distinct from the pre-post measures, so as to measure the transfer of skills from one setting to another (i.e., generalizability).

Rewarded Stop Signal task (15 minutes). The Stop Signal task provides a measure of reward approach motivation (Go reaction time) and ability to inhibit motor behavior (Stop reaction time) under conditions of high motivation to approach. An interesting dissociation emerges, such that some people (high reward sensitivity) are faster at going and worse at stopping under higher reward (76), some people (impulsive) are faster at going but worse at stopping (77), and others are faster at going but show no reward effect on stopping (78). In order to measure these individual differences, we have developed a version of the task in which participants are given information on the reward value of each upcoming trial, with 75% of (standard) trials awarded 2 points for correct performance, and 25% high reward trials receiving 50 points for correct performance (1). All participants start with a neutral block and then enter the reward block where they view stimuli of circles (Go), but some circles will have a ton played which indicates that no response should be given (Stop). A dual staircase tracking procedure is used, with a separate mean calculated for both the standard and the high reward trials. We specifically selected a version utilizing a cue at the beginning of each trial, as pretrial cues can modulate Go reaction time on both simple reaction time and stop signal reaction time paradigms (79, 80).

Decision-Making during Ambiguity (15 min). This is a financial decision-making task in which the amounts of favorable and unfavorable information regarding an ambiguous financial prospect will be parametrically manipulated (81). On each trial, participants are presented with a (distinct) virtual "bag"

of exactly 100 poker chips, all of which were colored either red or blue. For this bag, participants receive partial information about the number of red and blue chips in the bag. Parametrically varying the number of red chips and blue chips shown to participants allows for a trial-wise calibration of the availability of favorable or unfavorable information. Participants are asked to indicate whether they want to select a chip from the bag (giving them a chance to get a winning chip) or get 5 points for certain. The task consists of 56 trials. Each trial begins with a fixation cross, after which participants view the available information about the bag's contents versus the 5 point guarantee. Participants select which option they want for the current round by pressing the left or right key. Participants are not placed under time constraints for responding.

Paced Auditory Serial Addition Task (PASAT; 7 min) (82) The PASAT is a cognitive task purported to measure working memory, speed of information processing, and sustained and divided attention. It is a measure of many functional domains, but primarily relates to a participant's ability to persist in the face of emotional reactions (i.e., distress tolerance) to the task's demands. For this task, numbers are sequentially flashed on a computer screen, and participants are asked to add the presented number to the one previously presented. For example, if the digits '3', '6' and '2' were presented, the participant would respond with the correct sums, which are '9' and then '8'. Participants provide answers by using the mouse to click on the correct answer on a number pad displayed on the screen. Participants are told that their score increases by one point with each correct answer and that incorrect answers or omissions would not affect their total score. However, if they provide an incorrect answer or omitted a response, participants would hear a loud noise blast presented over headphones. The task consists of three levels with varying latencies between number presentations. Specifically, the first level of the PASAT provides a 3-s latency between number presentations (i.e., low difficulty) for 2 minutes, the second level provides a 2-s latency for the first 2 minutes and a 1-s latency for the last minute (i.e., medium difficulty), and the third level provides a 1-s latency (i.e., high difficulty) until terminated, up to 7 minutes.

Total Protocol Completion Time:

From consent to the completion of the study, participants will complete approximately 10-12 hours of study-related activities.

5. Genetic Testing N/A

6. **Subject Population:** Provide a detailed description of the types of human subjects who will be recruited into this study.

Participants will be 100 individuals (aged 18 and older) enrolled in outpatient (non-methadone/buprenorphine) treatment for any substance use disorder (other than PCP) at the Substance Abuse Treatment Unit in New Haven. As the goal of this project is to develop interventions that address self-regulation across multiple disorders, we will recruit individuals who have a range of substance use disorders and levels of severity. Otherwise, inclusion criteria are relatively broad and intended primarily to exclude individuals who are insufficiently stable to complete an outpatient trial of 4 weeks duration, who are highly unlikely to be located for assessment interviews, or who have a significant history of head injury or other condition that would confound interpretation of study findings. Individuals who are currently physically dependent on opioids, alcohol, or other substances and who require detoxification will be referred appropriately and invited to be re-screened following detoxification and stabilization. Completion of assessment instruments requires a minimum of a 4th grade reading level.

7. **Subject classification:** Check off all classifications of subjects that will be specifically recruited for enrollment in the research project. Will subjects who may require additional safeguards or other considerations be enrolled in the study? If so, identify the population of subjects requiring special safeguards and provide a justification for their involvement.

 Children	 Healthy	 Fetal material, placenta, or dead fetus
 Non-English Speaking	 Prisoners	 Economically disadvantaged persons
 Decisionally Impaired	 Employees	 Pregnant women and/or fetuses
 Yale Students	 Females of childbearing potential	

NOTE: Is this research proposal designed to enroll children who are wards of the state as potential subjects?

Yes No

8. **Inclusion/Exclusion Criteria:** What are the criteria used to determine subject inclusion or exclusion?

Inclusion and exclusion criteria

Participants will be included who:

- Are between ages 18 and 50.
- Meet current DSM-5 criteria for an alcohol, stimulant, cannabis, or opioid use disorder.
- Are sufficiently stable for 4 weeks of outpatient treatment.
- Are willing to provide locator information.
- Are fluent in English and have a 4th grader or higher reading level

Individuals will be excluded who:

- Meet DSM-5 criteria for a bipolar or schizophrenic disorder.
- Who have a legal case pending such that incarceration during the 4-week protocol is likely.
- Are physically dependent on alcohol, opioids or benzodiazepines or who report recent PCP use.
- Have a baseline Shipley estimated IQ less than 70
- Have 3 or more head injuries with loss of consciousness for over 30 minutes or lasting effects
- Have a history of chronic illness or neurological disorders (e.g., epilepsy or stroke) that would complicate evaluation of effects of cognitive training

9. How will **eligibility** be determined, and by whom? *Write here*

Following provision of written informed consent, baseline assessments will be completed with the research assistants. These will include demographic data, SCID interview for DSM-5, Shipley, and a brief medical history for determination of eligibility.

10. **Risks:** Describe the reasonably foreseeable risks, including risks to subject privacy, discomforts, or inconveniences associated with subjects participating in the research.

1. *Cognitive remediation training and control condition.*

Cognitive remediation is safe, inexpensive, portable, and easy to administer. The cognitive training tasks proposed here have been used safely with similar populations in previous work (1, 85). Thus, the potential dissemination of these treatments could be more efficient, cost-effective, and implemented in a wider variety of settings than traditional behavior change interventions. The

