Data will be collected, managed and analyzed through the standard procedures of the PDC as described in detail in the parent grant. Regarding statistical power, [name] previous study using a similar cognitive remediation battery (1) with 55 participants revealed an effect size of $d = .42$ for the malleability of performance on the training, with 92% power. A sample size of 100 will allow us to evaluate the effect of ongoing substance use as a moderator of treatment response at 80% power. We have established that we can recruit and treat a sample of this size in the one-year time allotment of the SOBC supplement. Our rates of end of treatment assessment and follow-up in Center trials is 90% or above, enabling us to conduct true intention to treat analyses with minimal statistical imputation (48, 49, 83). General Linear Modeling will be used to examine change in performance on these tasks over time. Using General Linear Modeling as we have in previous Center-supported studies (10, 37, 49, 57, 84), we will evaluate the extent to which participants who receive cognitive remediation show significantly greater improvement across time in the cognitive-affective assessment battery than those who receive the control training. Additionally, structural equation modeling (SEM) and latent profile analysis (LPA) will be used to examine variable-centered (correlation between measures) versus person-centered (profiles of individuals) alternatives. SEM with maximum-likelihood estimation will be used to test the association between pre-post measures and SUD-related behaviors. LPA, whereby each individual is assigned to a mutually exclusive assay class (i.e. profile) based on a data-driven analytic strategy, will be used to test the association between each individual's pre-post profile and treatment response. Moreover, we will use regression discontinuity analyses compare observations clustered closely on either side of a process-level threshold around a particular intervention. This analysis would allow us to examine the local average treatment effects on pre-post measures in a non-parametric data-driven manner.

Timeline	1	2	3	4	5	6	7	8	9	10	11	12
Recruit 3 participants/week	x	x	x	x	x	x	x	x	x			
Participant 100 completes 4 week treatment											x	
Participant 100 completes 1 month follow-up												x
Data analysis and preparation of reports												x

SECTION II: RESEARCH INVOLVING DRUGS, BIOLOGICS, RADIOTRACERS, PLACEBOS AND DEVICES

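### The primary aim spans several tasks, two visits and substance use, but no primary endpoint, visit, alpha or decision rule is named, so its false-positive rate is not controlled

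*Protocol*

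**What the plan says.** Protocol Section I.1 (Statement of Purpose) sets the primary Specific Aim as efficacy against control "on the indicators of cognitive-affective functioning and substance use", with the hypothesis that "individuals randomized to the cognitive remediation program will demonstrate improved functioning on the cognitive-affective battery as well as reduced substance abuse". Moderators are separately labelled exploratory, so the primary aim reads as confirmatory. The same section plans a "one-month follow-up, which will include assessment of substance use as well as the cognitive-affective battery".

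On the battery, Section I.4 (Baseline Cognitive-Affective Assessments) states: "This battery includes three tasks that have been previously used to tap the cognitive-affective processes associated with SUDs and other externalizing disorders". Only the incentivized n-back is described under that heading. For that task it adds "The primary dependent variable will be task performance", with no metric, load, incentive block or visit. Distress tolerance, BART and delay discounting are listed under the core battery of the parent center. The assessment schedule repeats all four performance tasks at Week 4 and at follow-up.

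On substance use, Section I.4 says: "Self-reports of substance use (cocaine, alcohol, opioids, marijuana, other illicit drugs, and nicotine) are documented at each contact via the Substance Use Calendar". Urine and breath tests are also scheduled. No summary variable is named.

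On analysis, Protocol Section I.13 and the SAP carry the same text. A general linear model is to assess whether the remediation arm will "show significantly greater improvement across time in the cognitive-affective assessment battery than those who receive the control training". Substance use is not named in that comparison. It enters only through a structural equation model of association. Section I.12 has the monitoring board track the availability of primary outcome data, which are never defined.

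**The concern.** An analyst who follows the plan must decide, after the data are in, which tasks make up the battery, which score represents each, which visit counts, and whether one significant result is enough. Nothing in either document settles these choices or bounds the error that comes with them.

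A significant difference on one task at one visit could then be reported as efficacy of the program, although such a result is not rare when there is no effect. A mixed or mostly null set of results would have no agreed interpretation.

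**Working it through.** **The plan's own figures.** No alpha or familywise error is stated, so there is none to reproduce. The design figure (100 participants, 80% power for a moderator) cannot be reproduced because no effect size is given. The prior-study figure (d = 0.42, 55 participants, 92% power) is matched by a one-sided paired t test (92.4%) or by a repeated-measures interaction with an assumed correlation of 0.6 (92.8%). A two-sided paired t test gives 86.4%. The intended sidedness cannot be read off from this.

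**Inputs from the documents.**
- Tasks: one described, three stated (Section I.4), four scheduled (assessment schedule).
- Post-baseline visits: two.
- Substance use: one outcome, if a single summary is chosen.

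**Assumptions.** Two-sided 5% per test. For correlated results, 0.2-0.5 between outcomes and 0.5-0.7 between visits.

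**Step 1: any one significant result suffices.** With k independent tests the error in either direction is 1 - 0.95^k. For benefit only it is 1 - 0.975^k. Correlated values come from 300,000 simulated multivariate normal draws.

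| Reading | k | Independent | Correlated | Benefit only, independent |
|---|---|---|---|---|
| n-back and substance use, one test each | 2 | 1 - 0.95^2 = 9.8% | 9-10% | 4.9% |
| Same, at each of two visits | 4 | 1 - 0.95^4 = 18.5% | 15-17% | 9.6% |
| Three tasks and substance use, one group-by-time test each | 4 | 18.5% | 16-18% | 9.6% |
| Four outcomes at two visits (four tasks, or three tasks and substance use) | 8 | 1 - 0.95^8 = 33.7% | 25-30% | 18.3% |
| Four tasks and substance use at two visits | 10 | 1 - 0.95^10 = 40.1% | 29-36% | 22.4% |

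The comparator for the last column is 2.5%. These counts are not a ceiling. The symptom and anxiety questionnaires are also repeated at both visits, the n-back has two loads and separate reward and punishment blocks, and the calendar covers six substance categories.

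**Step 2: both domains required, no effect anywhere.** Assume correlations of 0.3 between tasks, 0.6 between visits and 0.2 with substance use, and let any task-by-visit result plus any substance-use result count. The error is 0.95% with one task, 2.4% with three and 2.9% with four, all below 5%.

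**Step 3: both domains required, substance use truly improves.** Take the substance-use test as certain to succeed, which is the limiting case. The joint claim then rests on the battery alone. With the same correlations, the chance of a significant battery result under no battery effect is:
- one task: 5.0% (one test), 8.7% (two visits)
- three tasks: 13.6% (one test each), 22.9% (two visits)
- four tasks: 17.4% (one test each), 29.0% (two visits)

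**The case against.** A reader might infer that the plan lets the aim be claimed on any task, visit or substance-use result, with a 25-40% chance of a false efficacy claim. The documents do not support that, for five reasons.
- No passage says one result suffices, and the hypothesis joins the two domains as if both were expected.
- The larger test counts are constructions. The battery is said to have three tasks, not four. Improvement over time may mean one group-by-time test per outcome. Substance use is outside the stated between-arm model.
- The 40% figure needs ten independent tests, which repeated measures on the same people are not.
- Those rates count significance in either direction. A false claim of benefit is about half as likely.
- The Overview in Section I.4 gives the visits different roles: pre- and post-training testing for change in the cognitive-affective targets, and follow-up for durability and substance use.

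Both documents also defer to parent-grant procedures whose content on multiplicity is unknown here.

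All of this limits the size of the problem, but it does not supply a rule. Distinct roles for the visits are not a testing order. Requiring both domains still leaves open what counts as improvement on a battery of several tasks. The remark about the n-back's dependent variable does not make it the trial's endpoint.

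**Conclusion.** The omission stands: neither document fixes a primary endpoint, visit, alpha or decision rule across outcomes, and the content of the battery is inconsistent. The error rate of the primary claim is therefore uncontrolled, and its size depends on a rule that the plan does not give.

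If any one result sufficed, the error would lie between about 10% (two tests) and 40% (ten independent tests), with 16-19% for three tasks plus substance use tested once each. If both domains were required, it would be below 5% with no effect anywhere. In the limiting case where substance use truly improves, it would be about 14-29% for a false battery claim with three or four tasks. It stays at 5% in that case only if the battery is reduced to one test.

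The 5% level, its sidedness and all correlations are assumptions. No single one of these percentages can be called the trial's actual error rate.

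**What to change.** In Protocol Section I.13 and the SAP, before outcomes are compared by arm:
1. List the battery's tasks and reconcile the list with the stated three.
2. Name one primary test: the Week 4 difference between arms, adjusted for the Week 0 value, in one battery outcome at two-sided 5%. Settle now on either a mean z-score composite, with its tasks and scoring directions listed, or one stated n-back metric with load and incentive condition.
3. If that is significant, test one named substance-use summary at the one-month follow-up. If that is also significant, test durability of the battery outcome at follow-up. Each test is at two-sided 5% in this fixed order, which holds the familywise error of the three at 5%.
4. Report all single-task results as secondary, with Holm adjustment.

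The order of the second and third tests is a judgment the investigators may reverse, provided it is fixed in advance. The change affects wording only: enrollment, visits and treatment stay as they are. The cost is a stricter threshold for single-task claims, and a composite may dilute an effect confined to one task.
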